6.0 ESTIMATED PROJECT TIMELINE

The planned overall study period is 24 months, including study start up, IF booster, data collection, data matching, analysis, and reporting.

6.1 Table 2: Estimated Project Timeline

	Study Month						
	1-3	4-5	6	7-12	13-18	19-21	22-24
Study Preparation							
PRB Approval							
MOP, training development							
Data systems, eCRF development							
Train site research teams							
Regulatory approvals							
Implementation Facilitation							
EMR data abstraction			(Pilot)				
Participant enrollment and follow-up							
Data matching							
Qualitative interviews and focus groups							
Analysis and Reporting							
Data cleaning and data lock							
Data analysis							
Final study report and dissemination							

IF and support will continue for the sites during study development and start up. We are developing systems to retrospectively collect data on provision of BUP for the period of time between the parent study and the ancillary study. Prior to data collection, site teams will begin piloting data abstraction and approximately one-month of IF will commence to ensure that all clinical protocols, resources, and EMR programming is in place. Participant recruitment will begin once IF is complete and will take place over approximately 12 months, spanning a post-implementation period of six months and a maintenance period of six months. Full Study participants will complete a follow-up visit to assess engagement in treatment on the 30th day following ED discharge. The Day 30 follow-up visit will ideally occur no more than 7 days after this target, although outreach to reengage participants lost to contact may continue past this point. Data matching for the Limited Study participants will focus on the first 30 days following the index ED visit with evaluation continuing up to two years following study enrollment. Access to retrospective data one year prior to study enrollment will also be requested but will be optional.

7.0 STUDY POPULATION

The study population includes 4 sub-samples.

1. Qualitative: Stakeholders within and outside the hospital, including ED providers, hospital leadership, ED patients, ED staff, and community opinion leaders will be recruited to participate in the IF booster and qualitative focus groups and interviews.
2. ED patient process and outcome measures (administrative and health record data): Administrative and health record data for all adult ED patients will be examined to assess rates of screening, assessment, BUP eligibility determination, and other process measures. Further review of health records and administrative data matching to assess process/outcome measures (e.g., claims to assess linkage to treatment or filled prescriptions) will be performed in ED patients over the age of 18 screening positive for non-medical opioid use via a Waiver of Consent.
3. Full Study (Research visits): ED patients who are candidates to receive ED-initiated BUP and who meet additional study participation eligibility criteria (described below) will be recruited to participate in two research visits (at baseline and Day 30) and data matching.
4. Limited Study (Data matching only): ED patients who are candidates to receive ED-initiated BUP and who meet additional study participation eligibility criteria (described below) but who are unable or unwilling to participate in the Full Study will be invited to provide authorization for health services review and data matching with available registry, claims or administrative data.

7.1 Qualitative Population Eligibility Criteria

7.1.1 Inclusion Criteria

1. Be a key stakeholder or opinion leader for ED-initiated BUP at the hospital site or in the community, including but not limited to ED staff, ED patients, hospital leadership or community members.
2. 18 years of age or older.

7.1.2 Exclusion Criteria

1. Unwilling or unable to provide consent.
2. Currently in jail, prison or any inpatient overnight facility as required by court of law or have pending legal action or that could prevent participation in the study.

We estimate that approximately 24 stakeholders (approximately 8 at each site) will participate in interviews or focus groups at study close.

7.2 Full Study Population Eligibility Criteria

7.2.1 Inclusion Criteria

1. 18 years of age or older
2. Be able to speak English sufficiently to understand study procedures
3. Be a potential candidate for ED-initiated BUP by meeting either of the following two criteria:

- a. Clinical determination: Clinical documentation indicating the patient is a willing and eligible candidate for ED-initiated BUP or for whom this can be reasonably inferred, including any patient who receives ED-initiated BUP (via direct administration, prescription, or direct referral/transfer to BUP provider within 24 hours of ED discharge).
- b. Research determination: Both a and b below must be true at the time of study enrollment:
 - a) Assessment conducted by an RA indicates that the patient- (all must be true):
 - i. has had nonmedical opioid use within the last 7 days,
 - ii. meets DSM-5 criteria for moderate or severe OUD,
 - iii. denies methadone use within 72 hours of ED visit registration,
 - iv. is not engaged in formal MOUD treatment,
 - v. is not prescribed opioids for chronic pain management,
 - vi. reports being interested or “not sure” if interested in receiving BUP as elicited on the ED Health Survey during the index ED visit.
 - b) Absence of clinical documentation associated with the ED visit indicating that the patient is not a candidate for ED-initiated BUP.

7.2.2 Exclusion Criteria

1. Unwilling or unable to provide written informed consent/HIPPA Authorization for research procedures and/or consent for the release of health records and data matching for a period of 2 years following enrollment. Note that participants may opt-out of authorization for the 1 year prior to enrollment.
2. Currently engaged in formal MOUD treatment at the time of index ED visit.
3. Currently in jail, prison or any inpatient overnight facility as required by court of law or have pending legal action or that could prevent participation in the study.
4. Previous participation as a patient-participant in CTN-0079 or previous participation as a Full Study participant in the current study (Note: prior participation in Limited Study or qualitative inquiry does not preclude a patient from enrolling as Full Study participant.)
5. Presents from a medical-based extended care facility (e.g., skilled nursing facility)
6. Current research participant in a substance use intervention study.
7. Inadequate locator information (unable or unwilling to provide two unique means of contact).
8. Unable or unwilling to complete research visits at baseline and Day 30.

We anticipate that approximately 120 Full Study participants (approximately 40 per site) will be enrolled to complete research assessments and data matching within the 12-month recruitment timeline. We anticipate that as many as an additional 200 ED-BUP candidates will enroll in the Limited Study for a total N=320 for data matching outcomes.

7.3 Limited Study Population Eligibility Criteria

7.3.1 Inclusion Criteria

Inclusion criteria is the same as inclusion criteria above, for the Full Study. See section 7.2.

7.3.2 Exclusion Criteria:

1. Unwilling or unable to provide written agreement/HIPPA Authorization to participate and/or consent for the release of health records and data matching for a period of 2 years following enrollment. Note that participants may opt-out of authorization for the 1 year prior to study enrollment.
2. Currently engaged in formal MOUD treatment at the time of index ED visit.
3. Currently in jail, prison or any inpatient overnight facility as required by court of law or have pending legal action or that could prevent participation in the study.
4. Previous participation in the current study as a Limited Study or Full Study participant (Note: prior participation in qualitative inquiry does not preclude a patient from enrolling).
5. Presents from a medical-based extended care facility (e.g., skilled nursing facility).

7.4 Study Sites

The study is planned to be conducted in the three Emergency Departments that participated in the parent protocol:

1. Valley Regional Healthcare, Claremont, NH
2. Catholic Medical Center, Manchester, NH
3. Bellevue Hospital Center, New York, NY

For each site, clinical procedures including screening, BUP treatment initiation, and referral to ongoing care were approved and implemented between September - October of 2018.

8.0 STUDY OUTCOMES

Using mixed methods and triangulating multiple sources of data collected over the course of the parent and ancillary studies, we will evaluate the feasibility, acceptability, sustainability, and impact of the ED-initiated BUP clinical program and implementation facilitation strategy and identify factors influencing diffusion and effectiveness. Converging provider and patient perspectives and field notes with process measures and intervention outcomes, including proportions screened, treated, and engaged in treatment, will provide explanation to contextualize and better understand feasibility, acceptability, and factors associated with the rate with which the ED-initiated BUP innovation is adopted and how well it is sustained. Using directed content analysis, the qualitative interviews in conjunction with the qualitative inquiry conducted through CTN-0069/0079 and the patient-level factors and the granular level of data to be collected will allow us to better identify data pointing to the subgroups and specific stages of intervention where gaps exist as well as protective measures.

8.1 Primary and Key Secondary Outcomes

We have two primary outcomes to assess (1) clinical program implementation reach and (2) program effectiveness.

8.1.1 Program Implementation (Evaluation of Clinical Program Reach)

The primary implementation outcome is the proportion of patients receiving (i) ED-initiated/expedited BUP (primary analysis) and (ii) ED-initiated BUP (secondary analysis) amongst patients who are candidates to receive ED-initiated BUP.

Rationale: Our primary outcome is a measure of the success of a clinical protocol for identifying nonmedical opioid use and initiating treatment with BUP either directly through administration or prescription (i.e., ED-initiated BUP) or indirectly through transfer of care via “warm” referral to be seen within 24 hours for BUP treatment (i.e., ED-expedited BUP). We will conduct separate analyses for the composite measure of ED-initiated/expedited BUP and ED-initiated BUP (rationale discussed below). The efficacy of BUP is well-established across several domains including drug use, overdose, societal costs, quality-of-life and adherence to other ongoing treatments, e.g., for HIV. The ED is a meaningful setting in which to initiate treatment. The prevailing culture of the ED is that SUD is a non-emergent, chronic condition better addressed outside the ED where time and resources are less limited. Rarely do any components of Screening, Brief Intervention (whether brief advice, brief intervention, or initiation of treatment), or Referral for Treatment occur. Screening itself is not included in the clinical protocol elements of the largest emergency medicine organization, the American College of Emergency Physicians (ACEP), which are followed by over 200 healthcare systems. For these reasons, we have chosen to quantify rates of BUP initiation in the ED for the primary outcome and to evaluate downstream patient-level outcomes secondarily.

Description of the Measure and Methods:

- Receipt of ED-initiated/expedited BUP and Receipt of ED-initiated BUP (numerator) will be operationally defined to include: (1) administration of BUP in the ED, (2) prescription for BUP as part of the ED visit, or (3) provision of a specific “warm” referral or transfer of care to a provider, clinic, or treatment setting with the capacity to administer or prescribe BUP within no more than 24 hours. This measure will be abstracted from the health record primarily.

- Rationale: Adding ED-expedited BUP reflects contextual differences impacting the mode of treatment delivery identified through CTN-0079 (and, through informal comparison to CTN-0069 implementation trends). In large academic settings, the model appears to center on providers becoming BUP prescribers (i.e., obtaining DATA 2000 X-waiver). In some community ED settings (including sites outside of CTN-0079), however, particularly those with locum tenens staffing models, this model is less acceptable and less feasible. Instead, the emphasis often shifts from getting providers X-waivered to setting up streamlined, low barrier referral networks with urgent appointment availability. The addition of warm handoff for BUP treatment within 24 hours represents a patient-centered and context-centered good outcome for patients who are not yet in opioid withdrawal—as most ED providers do not have DATA 2000 X-waivers to prescribe BUP—and it is generally not acceptable (from the hospital, provider, and potentially the individual patient perspectives) to prolong patients' ED visit for the hours that may be necessary for an adequate state of opioid withdrawal to manifest so that BUP may safely be administered. As such, measures of quality that do not include ED-expedited BUP would not only miss this positive outcome but also potentially result in reduced performance and penalization related to contextual factors that may be outside of the control of the ED. The separate analysis of ED-initiated BUP (without ED-expedited BUP) is important to support harmonization of data to permit comparisons across studies in which this outcome is used, including CTN-0079. Also, ED-initiated BUP and ED-expedited BUP may not have equivalent effects on outcomes. Further study is needed to assess the potential differential impact the modes of treatment delivery have on outcomes.
- Operationally, ED-expedited BUP is a warm hand-off to a provider who can provide (dispense and/or/prescribe) BUP within 24 hours of discharge from the ED. To be included, there must be confirmation of this handoff, inclusive of clinical documentation in the EMR of medical decision making indicating that the patient is being handed off/referred for BUP treatment to a specific provider, clinic, or service with the capacity and availability to provide BUP within 24 hours of the patients' ED discharge. This could include a patient being given an appointment at a specific time and location, transfer to a provider, facility, or inpatient service directly from the ED, or through a pre-arranged follow-up mechanism in which a treating provider/facility has agreed to accept patients referred from the ED. Such agreements often exist to ensure access to urgent follow up care after ED discharge (for other medical problems and, more recently, OUD) as it may not be practical or possible to schedule appointments, particularly outside of traditional business hours. Neither confirmation of a completed appointment (i.e., patient shows up and is seen) nor receipt of BUP at the dedicated follow-up appointment will be required as privacy regulations may preclude our obtaining these data and as the patient and treating provider may elect to treat with alternative regimes (e.g., methadone, naltrexone).
- Candidate for ED-initiated BUP (denominator): In the parent study, the denominator included patients with clinical documentation of non-medical opioid use and documentation: (a) affirming eligibility and willingness to receive ED-initiated BUP (or for whom this could be reasonably be inferred) or (b) confirming receipt of BUP administered or prescribed as part of the ED visit. For the ancillary study, we will include all patients identified to have non-medical opioid use and exclude only those for whom there is documentation or other evidence of the patient *not* being eligible or willing to receive ED-initiated BUP (or for whom this could be reasonably be inferred). Rationale: The rationale for this change is that it should provide more complete capture (expect higher sensitivity and lower specificity) and hold the sites more accountable for ensuring

complete clinical documentation. All patients identified to have non-medical opioid use will be assumed to be candidates for ED-initiated BUP unless there is documentation indicating otherwise. In this way, inadequate documentation would be more likely to dilute positive outcomes rather than strengthen them. This outcome is somewhat analogous to a metric used as a Centers for Medicare and Medicaid Services (CMS) accountability measure of quality for treatment of pneumonia in EDs – the proportion of patients who receive antibiotic treatment for pneumonia within 4 hours of ED triage. The denominator includes all patients with diagnosis of pneumonia and excludes only patients for whom specific documentation exists indicating why antibiotics were not administered within 4 hours (e.g., patient refused, atypical presentation delaying diagnosis, etc.).

- Patients may be identified as candidates for ED-initiated BUP through EMR abstraction and/or through RA assessments embedded in health surveys using methods adapted from CTN-0069. This represents a change from the parent study, which was limited to EMR abstraction. RAs will approach patients in the ED to conduct health surveys embedded with questions to screen for non-medical opioid use and, if positive, assess for the main criteria for establishing one's eligibility and willingness to receive ED-initiated BUP (i.e., untreated, moderate to severe OUD; opioid use within 7 days; absence of common contraindications; interest in BUP treatment – as per section 7.2). Specific criteria of how to reconcile discrepant EMR and RA obtained data will be outlined in the MOP. Rationale: This additional means of identifying patients who are potentially eligible for ED-initiated BUP (and subsequent enrollment) will allow us to identify the target population in the event of diminished fidelity to clinical screening for non-medical opioid use. Further, we will use these data for quality assurance of clinical screening and secondary clinical assessments.

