2.0 STUDY SYNOPSIS

2.1 Clarification of Terminology

See below for a list of terminology used throughout this protocol, which are described and defined in more detail in section 8.0 and elsewhere in the protocol:

- Emergency Department (ED)-initiated Buprenorphine (BUP) clinical program refers to all the components of clinical care required to initiate treatment with BUP to ED patients with opioid use disorder (OUD) and provide them with access to ongoing treatment through referral. Site-specific clinical protocols were introduced in and by each clinical site/ED during the parent CTN-0079 study aided by study-sponsored subject matter expertise and other Implementation Facilitation (IF) activities. Each site-specific clinical protocol provides clinical guidance related to assessing a patient's "eligibility and willingness" to receive ED-initiated BUP (screening/identification followed by further assessments) and the other critical actions to treatment initiation and referral.
- ED-initiated BUP refers to BUP administered and/or prescribed to an ED patient as part of the ED visit. Referral to ongoing treatment should be provided to all patients receiving BUP treatment initiation.
- ED-expedited BUP refers to a patient being transferred directly or provided with specific "warm hand off" of care to a treatment setting or provider capable of prescribing or administering BUP within 24 hours of ED discharge. This includes direct transport or handoff to outpatient provider immediately from the ED, an appointment in clinic within 24 hours, or transfer to inpatient treatment. This indirect BUP treatment initiation is a means of providing expedited access to treatment for patients who are candidates for ED-initiated BUP but who are not in sufficient withdrawal to administer BUP and/or when there may or may not be a provider who has the DEA DATA 2000 "X-wavier" licensure required to prescribe BUP.
- ED-initiated/expedited BUP (abbreviation for "ED-initiated BUP and/or ED-expedited BUP") refers to a composite measure of either ED-initiated BUP and/or ED-expedited BUP occurring.

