Measure description: The treatment linkage/engagement measure must be confirmed by direct contact with the facility and/or treating clinician or other objective means (e.g., medical record review). Linkage to treatment for OUD will be defined as attendance at formal addiction treatment following the ED visit. Engagement in treatment for OUD will be defined as enrollment in formal addiction treatment on the 30th day following ED discharge. Formal addiction treatment will be those treatments consistent with the American Society of Addiction Medicine's (ASAM) level of care (1-4) and will include a range of clinical settings, including office-based providers of BUP or naltrexone, OTPs, intensive outpatient, inpatient, or residential treatments.

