8.2 Secondary Outcomes

Secondary Implementation outcomes will include other measures of reach, including evaluating ED-initiated BUP as a function of time. Other RE-AIM model dimensions to be assessed include Adoption (the proportion of providers who deliver ED-initiated/expedited BUP) and Implementation fidelity (proportions for adherence to clinical actions associated with the delivery of ED-initiated BUP). Maintenance will be assessed by evaluating these patient- and setting-level outcomes ≥ 6 months after the cessation of all study-supported IF (i.e., the Maintenance Period). As in the parent study, a range of secondary effectiveness measures will be assessed at the index ED and Day 30 visits for Full Study participants only, including but not limited to:

- Self-reported days of opioid and other drug use (TLFB)
- UDS results at 30 days post index ED visit
- Overdose events
- Healthcare utilization
- Quality of Life, Health, and Treatment Effectiveness (PROMIS-29, PHQ-9, TEA)
- Treatment satisfaction and acceptability

Process measures related to the clinical protocol include but are not limited to:

- Proportion of ED patients triaged who are screened for non-medical opioid use
- Proportion of patients screened who are positive for non-medical opioid use
- Among those positive:
 - Proportion of patients who are candidates to receive ED-initiated BUP
 - Proportion of patients who receive ED-initiated BUP (and the means of delivery, i.e., direct administration, prescription, or indirectly via warm referral within 24 hours)
 - Number meeting inclusion/exclusion criteria for ED-initiated BUP
 - DSM-5 moderate-to-severe OUD
 - Use opioids in past 7 days

- Not engaged in medication treatment for OUD
- Proportion who received facilitated referral for treatment amongst those who received some form of ED-initiated BUP.
- Fidelity
 - Critical actions completed

Implementation barriers and facilitators, include:

- Stakeholder acceptability over time (key informant interviews, focus groups)
- ED staff, patient, provider, community barriers and facilitators (key informant interviews, focus groups)

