12.3.3.2 Secondary Effectiveness Outcome Measures

The key secondary effectiveness outcome is linkage to formal addiction treatment for OUD within one week (operationalized at within 7-10 days). This is a binary outcome and will be defined as the proportion of participants with (objectively) confirmed linkage to formal addiction treatment for OUD within one week following ED discharge, amongst participants who received ED-initiated/expedited BUP. The outcome will be calculated as a pooled success rate over Post-IF and Maintenance periods.

Other secondary effectiveness analyses will evaluate the participant subgroups who received ED-initiated BUP and ED-expedited BUP separately as well as those who did not receive BUP.

As in the parent study, a range of secondary effectiveness measures will be assessed at the index ED and Day 30 visits, including but not limited to:

- Self-reported days of opioid and other drug use (TLFB)
- UDS results at 30 days post index ED visit
- Overdose events
- Healthcare utilization
- Quality of Life, Health, and Treatment Effectiveness (PROMIS-29, PHQ-9, TEA)
- Treatment satisfaction and acceptability

Process measures related to the clinical protocol include but are not limited to:

- Proportion of ED patients triaged who are screened for non-medical opioid use
- Proportion of those screened who are positive for non-medical opioid use
- Among those positive:

- Proportion who are candidates to receive ED-initiated BUP
- Proportion who receive ED-initiated BUP (and whether via direct administration, prescription, and/or warm referral within 24 hours)
- Numbers meeting inclusion/exclusion criteria for ED-initiated BUP
 - DSM-5 moderate-to-severe OUD
 - Use opioids in past 7 days
 - Not engaged in medication treatment for OUD
- Proportion who received facilitated referral for treatment amongst those who received some form of ED-initiated BUP.
- Fidelity
 - Critical actions completed

Implementation barriers and facilitators, include:

- Stakeholder acceptability over time (key informant interviews, focus groups)
- ED staff, patient, community barriers and facilitators (key informant interviews, focus groups)

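### Facilitated referral is met automatically by patients whose only form of BUP was ED-expedited, and a direct transfer can be both entry to the linkage denominator and the linkage itself; the plan separates neither

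*Combined protocol and SAP*

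**What the plan says.** **Exposure.** Section 2.1 describes ED-expedited BUP as a warm hand-off to a setting able to provide BUP within 24 hours: "This includes direct transport or handoff to outpatient provider immediately from the ED, an appointment in clinic within 24 hours, or transfer to inpatient treatment". The operational definition in 8.1.1 gives three routes: a specific appointment, a "transfer to a provider, facility, or inpatient service directly from the ED", or a pre-arranged follow-up mechanism. For the exposure, attendance is waived: "Neither confirmation of a completed appointment (i.e., patient shows up and is seen) nor receipt of BUP" at the follow-up is required. Section 2.1 defines the composite with and/or, so one patient can have both modes.

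**Linkage (key secondary effectiveness outcome).** Section 8.1.2: "Linkage to treatment for OUD will be defined as attendance at formal addiction treatment following the ED visit". It "must be confirmed by direct contact with the facility and/or treating clinician or other objective means". Formal addiction treatment covers ASAM levels 1-4, including office-based BUP providers, opioid treatment programs, and inpatient and residential care. The denominator (8.1.2, 12.3.3.2) is participants who received ED-initiated/expedited BUP. Loss to follow-up counts as failure (12.10).

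**Facilitated referral (process measure).** Sections 8.2 and 12.3.3.2: "Proportion who received facilitated referral for treatment amongst those who received some form of ED-initiated BUP". The same lists name direct administration, prescription and warm referral within 24 hours as the means by which ED-initiated BUP is delivered.

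**Use of the modes.** Section 12.3.3.2: "Other secondary effectiveness analyses will evaluate the participant subgroups who received ED-initiated BUP and ED-expedited BUP separately". Section 8.1.1 says that the modes may differ in effect and that this needs further study. No contrast between them is specified.

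**The concern.** Two measures overlap with the event that defines their own denominator.

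For facilitated referral, a warm referral is what makes a patient ED-expedited. If it also counts as a form of ED-initiated BUP, every patient with only that form passes. The pooled rate then rises with the expedited share, even if referral of patients given or prescribed BUP does not change. As a fidelity measure it would partly report the site's delivery model.

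For linkage, the overlap is confined to direct transfer. A patient moved from the ED into formal addiction treatment enters the denominator through that transfer and attends treatment through the same transfer. Pooled linkage, and the linkage rates shown separately for the two modes, then depend partly on how many hand-offs were transfers. A reader who sets the two mode rates side by side could take a difference in route mix for a difference in how well patients go on to reach treatment after leaving the ED.

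The listed sensitivity analyses do not separate this. Excluding referrals (8.3, 12.7) is a permutation of the reach outcome. The linkage permutations change the time window, the data source or the inclusion of non-recipients. In the 72-hour version an index transfer would still count while later linkages drop out.

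**Working it through.** **The plan's own figure.** The only design figures for these outcomes are in 12.5.3: 90th-percentile 95% CI widths below 0.2 (implementation) and 0.3 (effectiveness). I simulated the 12.5.1 estimator with equal sites, no site difference and 10,000 iterations. The largest widths were 0.142 (N=180) and 0.111 (N=300) for implementation, and 0.235 (N=60) and 0.172 (N=120) for effectiveness. The stated bounds reproduce. The point does not depend on them; they serve only as a yardstick.

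**Inputs for linkage.**
- L, underlying linkage for everyone not directly transferred, equal in both modes: 0.30 to 0.40. Section 8.1.2 cites approximately 30-40% from an existing ED program; its use here is an assumption.
- e, ED-expedited share of recipients: assumed 0.10 to 0.50.
- t, direct-transfer share of ED-expedited patients: assumed 0.10 to 0.50.
- Direct transfers are taken as 100% linked, that is, all into formal addiction treatment and all confirmed. This is the upper limit.
- The modes are treated as exclusive and site weighting is ignored, for simplicity.

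**Formulas.**
- ED-expedited linkage = t + (1 - t)L
- Gap between modes = t(1 - L)
- Pooled linkage = (1 - e)L + e[t + (1 - t)L] = L + e·t(1 - L)

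**Results at L = 0.35, e = 0.25** (ED-initiated linkage is 0.35 throughout):

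| t | ED-expedited | Gap | Pooled |
|---|---|---|---|
| 0 | 0.350 | 0 | 0.350 |
| 0.10 | 0.10 + 0.90×0.35 = 0.415 | 0.065 | 0.366 |
| 0.25 | 0.25 + 0.75×0.35 = 0.5125 | 0.1625 | 0.391 |
| 0.50 | 0.50 + 0.50×0.35 = 0.675 | 0.325 | 0.431 |

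**Range.** Smallest gap 0.10×0.60 = 0.06; largest 0.50×0.70 = 0.35. Smallest pooled increase 0.10×0.10×0.60 = 0.006; largest 0.50×0.50×0.70 = 0.175. Both are zero at t = 0.

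**If someone tested the gap.** Section 12.6 permits univariate tests in general and 12.8 sets 5% (two-sided assumed). Suppose all 120 Full Study participants were recipients, split 90 and 30. With L = 0.35 in both modes, a two-proportion test would show a difference with probability about 0.10, 0.35 and 0.89 for t = 0.10, 0.25 and 0.50.

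**Facilitated referral.** Let R be the rate among patients given or prescribed BUP (assumed), and let e now be the share whose only form was ED-expedited. The measure reads (1 - e)R + e.

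| R | e = 0.10 | e = 0.25 | e = 0.50 |
|---|---|---|---|
| 0.50 | 0.55 | 0.625 | 0.75 |
| 0.70 | 0.73 | 0.775 | 0.85 |
| 0.90 | 0.91 | 0.925 | 0.95 |

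**The case against.** Linkage is a program outcome. A patient who is transferred and arrives did reach treatment, so counting that is correct, and dropping such patients would discard part of what ED-expedited BUP does. This stands: it is why the pooled definition should stay and the exclusion should be only a sensitivity analysis.

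A reader might infer that linkage is met by definition for ED-expedited patients as a group. The documents do not support that. The appointment and pre-arranged routes count as exposure without attendance, while linkage requires attendance. Even for transfers, linkage needs objective confirmation, and an inpatient service need not be formal addiction treatment.

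A reader might also infer that the plan contains a biased comparison of the two modes. It does not: the subgroups are evaluated separately, 12.4 makes the linkage analysis descriptive, and no contrast is named. The problem arises only when the rates are read against each other. Because the modes can overlap, transfer is not tied to one side either.

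The effect may be small. At t = 0.10 and e = 0.25, pooled linkage moves 1.6 points, against an interval width of about 17 points at N=120. Section 9.4.1.1 also expects patients admitted to a treatment program to be harder to reach, which could lower the transfer share among those enrolled.

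On facilitated referral, 2.1 limits ED-initiated BUP to BUP administered or prescribed. Read that way the measure is not circular, but the lists in 8.2 and 12.3.3.2 use the wider sense and facilitated referral is not defined separately. Counting a warm referral as a referral is correct for the individual patient; the difficulty is a denominator selected on it.

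**Conclusion.** The point holds in two limited parts. On a plain reading of 8.2 and 12.3.3.2, facilitated referral is automatic for patients whose only form was ED-expedited BUP. With an assumed 70% among the others, the measure would read 73% to 85% for ED-expedited-only shares of 10% to 50%. For direct transfers only, and subject to confirmation, the qualifying event and the linkage event can be the same. Under the assumed ranges that produces a gap between modes of 6 to 35 points and adds 0.6 to 17.5 points to pooled linkage. The documents give neither the expedited share nor the transfer share, so the actual size is unknown and could be nil.

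It would be tempting to extend this to the primary effectiveness outcome. Engagement requires confirmed enrollment in treatment on day 30, which a transfer on day 0 does not satisfy by definition. The stated precision is also unaffected. This is a matter for a key secondary outcome and one process measure.

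**What to change.** 1. In 8.2 and 12.3.3.2, limit the facilitated-referral denominator to patients whose BUP was administered or prescribed, including those also handed off.
2. In 8.1.2 and 12.3.3.2, keep pooled linkage as defined and state that an index transfer into formal addiction treatment, once objectively confirmed, counts as linkage.
3. Tabulate linkage by route: administered or prescribed only, appointment, pre-arranged hand-off, and direct transfer. Set a rule for patients with both modes, for example a separate row.
4. Wherever ED-initiated and ED-expedited linkage rates are set side by side, add a sensitivity analysis without direct transfers, labelled as describing patients who were not moved straight into treatment.

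The cost is outcome wording, one extra tabulation and one sensitivity analysis. No new data collection should be needed: 8.1.1 already requires the hand-off to be documented in the medical record, and the Facility survey (10.5) records admission date and level of care. The drawback is that some route cells will be small with about 120 participants, so those rates should be read as descriptive.
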